- All patients of the Center for Urogynecology and Pelvic Reconstructive Surgery in the Department of Obstetrics/Gynecology and Women's Health Institute at the Cleveland Clinic (Main Campus, Fairview Hospital, Hillcrest Hospital, Medina Hospital and Beachwood Ambulatory Surgery Center) scheduled to undergo major or minor surgery for pelvic organ prolapse and/or urinary incontinence
 - Major surgery⁺
 - Minimally invasive (laparoscopic or robotic) sacrocolpopexy
 - Vaginal colpopexy (intraperitoneal or extraperitoneal)
 - Vaginal or minimally invasive (laparoscopic or robotic) hysteropexy (uterine suspension)
 - Obliterative procedures (colpocleisis)
 - Additional procedures accompanying the above major operations may include: hysterectomy (total or supracervical), trachelectomy, salpingectomy or salpingo-oophorectomy, anterior and/or posterior colporrhaphy with perineorrhaphy, enterocele repair, minimally invasive Burch colposuspension or paravaginal defect repair, vaginal mesh removal or revision, placement of vaginal graft, or placement of mid-urethral sling
 - Minor surgery
 - Isolated colporrhaphy (anterior/posterior) and/or perineorrhaphy
 - Placement of mid-urethral sling
 - Vaginal mesh removal or revision
- Inclusion Criteria
 - Age greater than 18 years old
 - Has technological capability to participate in videoconferencing (high-speed internet access with desktop computer or mobile device)
 - Has decision-making capacity and able to provide informed consent for research participation
 - Able to speak and read English
- Exclusion Criteria
 - Patient requested to physically come in the office or have a virtual visit for her postoperative visit
 - Planned concomitant surgery with another surgical team
 - Office follow-up is deemed medically necessary by provider/surgeon

Study Procedures

- Screening and Recruitment
 - Participants will be prospectively identified by the primary surgeon during the patient's initial consultation when the decision is made to proceed with surgery for pelvic organ prolapse and/or urinary incontinence.

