 - Compensation will be provided to trial participants with a total of \$50 in the form of a check in the mail from Cleveland Clinic. The payment will be prorated according to the procedures completed. The participant will receive \$10 after completion of the Patient Preparedness Questionnaire pre-operatively, \$20 after completion of the Patient Satisfaction Questionnaire-18 postoperatively, and \$20 after completion of the Patient Postoperative Visit Questionnaire postoperatively. Addresses for mailing of checks will be verified.
 - Reasons for declining participation in the study will be collected and recorded separately.

- Consent/Accent Process
 - Patients who agree to participate will sign a consent form. The consent interview will occur during the participant's preoperative visit at the Center for Urogynecology and Pelvic Reconstructive Surgery at Cleveland Clinic. Alternatively, the patient will be able to provide consent for research participation remotely via electronic signature using the DocuSign eConsent Platform.
- Randomization:
 - Trial participants will be randomized to one of two arms:
 - 1) **Office Visit (Control Arm):** Patients randomized to the control arm will be scheduled for and follow up with the surgeon or an advanced practice provider via an in-office visit at 6 weeks after the planned date of surgery. If the surgery were to be rescheduled to a future date, the postoperative visit will be moved accordingly to ensure follow-up occurs at the 6-week postoperative period.
 - 2) **Virtual Visit (Intervention Arm):** Patients randomized to the intervention arm will be scheduled for and follow up with the surgeon or an advanced practice provider via a virtual visit using videoconference technology at 6 weeks after the anticipated date of surgery. If the surgery were to be rescheduled to a future date, the postoperative visit will be moved accordingly to ensure follow-up occurs at the 6-week postoperative period.

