 - Stratified block randomization will be used to ensure that the number of participants is equally distributed among the study groups and stratified by surgery level (major, minor). The allocation sequence will be generated with block size of 4 using computer software. Randomization will be implemented with the REDCap Randomization module. Randomization schedule can only be accessed by a research personnel not directly involved in patient care. The patient's 6-week postoperative visit will be scheduled according to her assigned group.
- Study instruments:
 - Study instruments will be administered at the preoperative visit and the 6-week postoperative visit. The questionnaires for this study include the Patient Preparedness Questionnaire (PPQ), the Patient Satisfaction Questionnaire-18 (PSQ-18), and modified patient and provider preference questionnaires entitled, Patient Postoperative Visit Questionnaire and Provider Postoperative Visit Preference Questionnaire.
 - The PPQ will be administered during the preoperative visit to assess patient knowledge and preparedness for surgery, which has been demonstrated in other studies to impact postoperative satisfaction, perceived complications, and drug utilization.¹⁰⁻¹¹ The PPQ is a 11-item questionnaire scored on a six-point Likert scale and has responses ranging from 1 (strongly agree) to 6 (strongly disagree).⁹ The questionnaire for this study will utilize the same six-point scale with a reversed scoring system, ranging from 1 (strongly disagree) to 6 (strongly agree). Although there are currently no validated measures to assess surgical preparedness in urogynecology, the PPQ has been used in several studies assessing surgical preparedness in women undergoing pelvic organ prolapse and/or stress urinary incontinence.^{8,12} These studies utilized the same cutoff score for question 11 (i.e., an answer of "strongly agree" to the question "overall, I feel prepared for my upcoming surgery") to define meeting criteria for preoperative preparedness.
 - The PSQ-18 will be administered after the 6-week postoperative virtual or in-office visit to assess patient satisfaction with their postoperative visit. The PSQ-18 is a

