- All questionnaires can be completed either with paper forms or electronically through Research Electronic Data Capture (REDCap), depending on patient/provider preference. Study participants will be reminded within 48 to 72 hours after their visit regarding completion of their questionnaires by telephone call using a standardized phone script or by text or email message after their preoperative visit and their 6-week postoperative visit. Reminders for survey completion will be sent up to two times.

- Preoperative Visit
 - The preoperative visit will take place per our standard protocol, which includes a thorough discussion of the surgical purpose, alternatives, benefits, risks/complications, and postoperative expectations. Following informed consent, study-related procedures during the preoperative visit include study randomization, and scheduling of postoperative visits per study protocol. The PPQ will also be administered during this visit.
- Postoperative Visit (6 weeks)
 - Prior to the 6-week postoperative visit, a study investigator will initiate a reminder to the participant by phone, email or text to remind her of her upcoming appointment using a standard script. A checklist of discussion points will be used to standardize counseling and evaluation during the 6-week postoperative visit. Both office and virtual visits will be conducted in the same manner: The provider

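### One fixed block size of 4, in an unblinded trial with a discretionary surgeon exclusion, makes up to a third of assignments deducible and leaves an avoidable risk of selection bias

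*Combined protocol and SAP*

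**What the plan says.** All references are to the combined protocol and SAP.

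- **Sequence.** Section C, Study Procedures, Randomization: "The allocation sequence will be generated with block size of 4 using computer software". Allocation is 1:1 within two strata, major and minor surgery. Neither surgeon nor facility is a stratifier. No variation in block size is described.
- **Concealment of the list.** Same section: "Randomization schedule can only be accessed by a research personnel not directly involved in patient care".
- **Visibility of the arm.** Same section: "The patient's 6-week postoperative visit will be scheduled according to her assigned group". Under Preoperative Visit, "study-related procedures during the preoperative visit include study randomization, and scheduling of postoperative visits per study protocol", so assignment and booking happen together. Patients in the intervention arm "follow up with the surgeon or an advanced practice provider via a virtual visit using videoconference technology", so the treating team knows the arm. No blinding is described.
- **Discretion over entry.** Under Screening and Recruitment: "Participants will be prospectively identified by the primary surgeon during the patient's initial consultation". One of the exclusion criteria reads "Office follow-up is deemed medically necessary by provider/surgeon". No objective criteria are listed for it, and no time is given by which the judgement must be settled.
- **Numbers.** Section D, Power Analysis and Sample Size Calculation, gives an enrolment target of 106. Section C, Overall Study Design, gives a 15-month recruitment period ending 31 March 2024.

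**The concern.** Restricting access to the schedule stops staff from looking up the next assignment. It does not stop them from working it out. In a block of four with two places per arm, once both places of one arm are used, the rest of the block is known. Here the block size is printed in the protocol, there are only two sequences, and each assignment becomes visible when the visit is booked.

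Predictability matters only if someone can act on it before the patient is randomized. The exclusion for medically necessary office follow-up provides that opening. It rests on judgement, it is exercised by the clinicians who recruit, and the documents do not tie it to a moment before the next assignment could be guessed.

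At stake is the comparability of the two groups. The primary outcome is a self-reported satisfaction score, and the intention-to-treat analysis cannot repair selection that takes place before randomization.

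**Working it through.** The plan gives no predictability figure to reproduce, so the check starts from its design inputs: block size 4, 1:1 allocation, two strata (section C, Randomization), and 106 participants (section D).

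**1. Ceiling: full history of the stratum and known block boundaries.** There are 6 equally likely orderings of a 2:2 block. The chance that the next assignment is already certain is:
- positions 1 and 2: 0
- position 3: 1/3 (the first two went to the same arm)
- position 4: 1

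Mean = (0 + 0 + 1/3 + 1)/4 = 1/3 = 33.3%. For 106 participants, 106 × 1/3 = 35.3, or about 35.

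**2. Best-guess accuracy under the same conditions.** Always guessing the arm with more places left is right with probability 1/2, 2/3, 2/3 and 1 at positions 1 to 4. Mean = (1/2 + 2/3 + 2/3 + 1)/4 = 17/24 = 70.8%, against 50% by chance.

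**3. Partial view of past assignments.** Suppose each past assignment is seen independently with probability q, and block boundaries are still known. Certainty then requires that both used places of one arm were seen, so the share is (q²/3 + q²)/4 = q²/3. The values of q are assumptions.

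| q | Certain share |
|---|---|
| 100% | 33.3% |
| 75% | 18.8% |
| 50% | 8.3% |
| 25% | 2.1% |

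**4. Lag between the surgeon's decision and randomization.** If one other patient in the stratum is randomized in between, only position 4 can be certain, and only when the first two assignments matched: (1/3)/4 = 1/12 = 8.3%. If two or more intervene, at most one assignment in the block is known, and the share is 0.

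The documents do not give the lag. As an illustration, 106 patients over 15 months is about 7.1 per month. With an even split between strata and Poisson accrual (both assumed), about 0.81 patients per stratum are randomized per week. With m the expected number intervening, the share is e^(−m)/3 + m·e^(−m)/12:
- 1 week (m = 0.81): about 18%
- 2 weeks (m = 1.63): about 9%
- 4 weeks (m = 3.25): about 2%

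**5. Randomly varying block sizes.** Simulated for an observer who knows the set of sizes and the full history of the stratum, with 53 patients per stratum assumed:

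| Block sizes | Certain share | Best-guess accuracy |
|---|---|---|
| 4 only | 32.6% | 70.5% |
| 4 and 6 | about 5.5% | about 69% |
| 4, 6 and 8 | about 2.3% | about 68% |

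The first row is slightly below 1/3 because the last block is incomplete. Varying the size removes most certain predictions but hardly changes the advantage in guessing.

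**The case against.** The strongest reply is that a third is a ceiling nobody is likely to reach, and that stands. Patients come from five facilities and the sequence is not stratified by surgeon, so one surgeon would usually see only part of a stratum. A booking alone does not identify a trial patient, because patients outside the trial may also have either type of visit. The observer must also know who is enrolled, in which stratum, and where blocks begin. Identification at the initial consultation precedes randomization, which weakens foreknowledge at that step.

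This limits the point without removing it. Scheduling staff are briefed on the project (section H), and all involved study staff meet monthly to compare satisfaction between arms (section G), so some people may see more of the sequence than a single surgeon. Nothing in the plan prevents a later exclusion at the preoperative visit.

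A reader might also infer that the bias would favour noninferiority, with patients expected to do poorly on video kept out of virtual slots. The documents do not support that. Nothing in them shows that surgeons would screen in that direction, and selective exclusion ahead of office slots would push the result the other way. Nor do they give any basis for putting a size on the effect in PSQ-18 points.

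**Conclusion.** The point holds as an avoidable weakness in allocation concealment. The fixed block size, the visible arm and the discretionary exclusion are all in the document, and restricted access to the schedule does not prevent deduction from past assignments.

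At most 33% of assignments (about 35 of 106) could be known with certainty, and only with complete stratum history and known block boundaries. Under the partial-view assumptions the share is about 19%, 8% or 2%. It is 1/12 or zero once one, or two or more, other patients in the stratum are randomized between decision and randomization.

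It would be wrong to read this as 35 assignments that staff will in fact foresee, or as evidence that selection has occurred. The finding is a risk of selection bias whose direction and size are not established. It does not affect the sample size calculation.

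**What to change.** 1. For all patients not yet randomized, generate the REDCap allocation table with randomly varying block sizes (for example 4 and 6, or 4, 6 and 8) within each surgery-level stratum.
2. Keep the block sizes out of documents that clinical staff see.
3. Because guessing stays nearly as accurate, log the surgeon's judgement on the need for office follow-up, with its reason, at the initial consultation. Log any later exclusion with its date and reason. Recording the decision merely before the assignment is released is not enough, since it does not stop someone who has already deduced the arm.
4. If enrolment is complete, which the planned recruitment dates make possible, report the fixed block size and the number and timing of discretionary exclusions as a limitation.

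The cost is small: a regenerated table, a short log alongside the record of reasons for declining that the protocol already keeps, and slightly larger possible imbalance at the end of the trial. The largest difference between arms within a stratum is half the largest block: 2 patients with blocks of 4, 3 if blocks of 6 are included, and 4 if blocks of 8 are included.

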We hypothesize that patient satisfaction with a virtual postoperative visit will be noninferior to patient satisfaction with an in-office postoperative visit

Secondary aims:

- To compare healthcare resource utilization after the postoperative visit up to 12 weeks following urogynecologic surgery between patients receiving in-office versus virtual-video postoperative visits.

We hypothesize that the virtual group will be noninferior to the in-office group based on healthcare resource utilization after the postoperative visit up to 12 weeks following surgery.

- To compare adverse events after the postoperative visit up to 12 weeks following urogynecologic surgery between patients receiving in-office versus virtual-video six-week postoperative visits.

We hypothesize that the virtual group will be noninferior to the in-office group based on adverse events after the postoperative visit up to 12 weeks following surgery.

- To evaluate patient and provider preferences/attitudes toward in-office versus virtual-video postoperative visits

C. RESEARCH PLAN

Overall Study Design

- The study is a randomized controlled noninferiority trial evaluating patient satisfaction with in-office versus virtual-video postoperative visits at six weeks following urogynecologic surgery. We aim to assess whether the intervention of virtual postoperative visit via videoconference technology is noninferior to the standard/traditional in-office postoperative visit for our primary outcome of patient satisfaction. The recruitment period will be 15 months (January 1, 2023 to March 31, 2024). The follow-up period for each participant will be 12 weeks after surgery.

Outcome Measures

- Primary Outcome:
 - Patient satisfaction as measured by the Patient Satisfaction Questionnaire-18 at the 6-week postoperative visit
- Secondary Outcomes:
 - Healthcare resource utilization as measured by patient-initiated phone calls, unscheduled in-person/virtual office visits, emergency room or urgent care visits, and inpatient readmissions after the scheduled postoperative visit up to 12 weeks following surgery
 - Adverse events after the scheduled postoperative visit up to 12 weeks following surgery
 - Patient and provider preferences/attitudes toward virtual or office visits

Eligibility Criteria

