will inquire about any concerns the patient has regarding recovery, followed by any unanticipated healthcare encounters at outside facilities. These outside healthcare encounters will be documented by the provider in their Epic note to facilitate data collection by the study investigators. The provider will review key aspects of postoperative care (bowel function, urinary function, presence of vaginal bleeding, dietary status, and ambulatory status), postoperative instructions and precautions, findings and procedures done during surgery, and pathology results (if applicable). The provider will then visually examine surgical sites and document their findings in their Epic note. The provider will inquire about any additional questions from the patient and perform additional evaluation/treatments per standard of care. The PSQ-18 and the Patient Postoperative Visit questionnaire will be administered after this visit. The patient may be contacted for up to two times by a study investigator via phone, text or email within 48 to 72 hours after the visit regarding completion of study questionnaires using a script.

- **Provider Recruitment and Study Procedures**
 - Surgeons and advanced practice providers will be educated about the study during the Urogynecology Section Research Meeting as part of the provider recruitment process.
 - After the six-week virtual or in-office visit, the provider will fill out the Provider Information Sheet and the Provider Postoperative Visit Preference Questionnaire. The provider will complete the questionnaire at the end of the visit. If this is not feasible, the provider will be sent a text reminder for up to two times to their Cleveland Clinic issued phone number within 48 to 72 hours after the visit.

	Preoperative Visit	Day of Surgery	Postoperative Visit (6 weeks)	End of study follow-up (12 weeks after surgery)
Questionnaire: PPQ	X			
Questionnaire: PSQ-18			X	
Questionnaire: Patient Postoperative Visit			X	
Questionnaire: Provider Postoperative Visit Preference			X	
Data collection: Demographic and baseline clinical characteristics	X			
Data collection: Perioperative characteristics		X		
Data collection: Postoperative healthcare resource utilization, adverse events			X	X

D. DATA ANALYSIS PLAN

- Data Collection

- A) Demographic data will include the following:
 - Date of preoperative visit (MM/DD/YYYY)
 - Route of preoperative visit with surgeon (in-office/virtual)
 - MRN
 - Age (years)
 - Race
 - Ethnicity

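### Mode, place and delay of completing the primary PSQ-18 may differ by arm, and the plan neither equalises nor records them

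*Combined protocol and SAP*

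**What the plan says.** Outcome Measures (section C) defines the primary outcome as "Patient satisfaction as measured by the Patient Satisfaction Questionnaire-18 at the 6-week postoperative visit".

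On timing, the Study instruments text says both "Study instruments will be administered at the preoperative visit and the 6-week postoperative visit" and "The PSQ-18 will be administered after the 6-week postoperative virtual or in-office visit to assess patient satisfaction with their postoperative visit". The Postoperative Visit (6 weeks) text adds: "The PSQ-18 and the Patient Postoperative Visit questionnaire will be administered after this visit". The schedule table marks the PSQ-18 under the 6-week visit. None of these gives a time limit or a place.

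On mode, the Study instruments text says: "All questionnaires can be completed either with paper forms or electronically through Research Electronic Data Capture (REDCap), depending on patient/provider preference".

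On setting, the Randomization text has control patients seen "via an in-office visit at 6 weeks after the planned date of surgery" and intervention patients "via a virtual visit using videoconference technology at 6 weeks after the anticipated date of surgery".

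On follow-up of unreturned forms: "The patient may be contacted for up to two times by a study investigator via phone, text or email within 48 to 72 hours". This applies to both arms, as does the $20 paid for completing the PSQ-18 (Screening and Recruitment).

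**The concern.** The PSQ-18 covers interpersonal manner, communication, technical quality and time spent with the doctor, so it partly rates the provider the patient has just seen. Patients cannot be blinded to the type of visit. With such an outcome, the way the answer is collected can affect the answer.

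Under the stated rule an office patient may be given a paper form and complete it in the clinic. A virtual patient has no such option. Any difference this makes arises after randomisation and follows the arm, so randomisation does not balance it. The virtual-minus-office difference would then combine the effect of the visit type with the effect of how satisfaction was collected. In a noninferiority comparison with a 5-point margin, a shift of 1 or 2 points is 20% to 40% of the margin.

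**Working it through.** **1. Does any text equalise the procedure?** The Study instruments section leaves mode to preference. The timing texts say at or after the visit. The statement that both kinds of visit are conducted in the same way (Postoperative Visit (6 weeks)) introduces the content of the visit: concerns, review of recovery, examination. It does not cover completion of the questionnaire. The reminders are common to both arms, but they fix neither mode, place nor time of completion.

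**2. Could the issue be examined afterwards?** The six-week data list (section D, Data Collection, part C) records the route of the visit, crossover, technical difficulties and the type of provider. It does not list date, mode or place of PSQ-18 completion. The Statistical Analysis section has no sensitivity analysis for mode or timing.

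**3. The plan's own figure.** Inputs from Power Analysis and Sample Size Calculation: margin 5, SD 10, 80% power, significance level 0.05, 50 per group.

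n per arm = 2 × SD² × (z_alpha + z_power)² / margin²

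- One-sided 0.05: 2 × 100 × (1.645 + 0.842)² / 25 = 49.5, so 50 per arm and 100 in total. With 5% attrition, 100 / 0.95 = 105.3, so 106. Both stated figures reproduce.
- One-sided 0.025, which matches the two-sided 95% confidence interval rule in Statistical Analysis: 62.8, so 63 per arm. The starting power of about 70% below comes from this mismatch, which is a separate matter.

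**4. Illustration of a setting effect.** The documents give no size or direction. Let b be an assumed shift in virtual minus office caused by the collection setting. With 50 per arm and SD 10:

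SE = 10 × √(2/50) = 2.0

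P(noninferiority declared) = Φ((5 + true difference + b) / 2.0 − 1.96)

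| Assumed b (points) | True difference 0 | True difference -5 |
|---|---|---|
| -2 | 32.3% | 0.2% |
| -1 | 51.6% | 0.7% |
| 0 | 70.5% | 2.5% |
| +1 | 85.1% | 7.2% |
| +2 | 93.8% | 16.9% |

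With the noncentral t distribution (98 degrees of freedom), the first column gives 69.7%, 50.8% and 31.8% at b = 0, -1 and -2. The second gives 7.1% at b = +1.

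The pattern does not depend on the alpha question. At one-sided 0.05 (normal approximation), the chance at a true difference of 0 falls from 80.4% to 63.9% (b = -1) or 44.2% (b = -2). False noninferiority rises from 5% to 12.6% (b = +1).

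**5. What a shift of this size would take.** If half the office patients answered on site (assumed), a 1 to 2 point rise in the office mean needs a rise of 2 to 4 points in those patients: 0.5 × 2 = 1 and 0.5 × 4 = 2.

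**The case against.** The strongest reply is that much of this is inferred from silence. The documents say after the visit, not immediately after it, and name no place of completion. Reminders are planned for participants generally, so some office patients will also answer from home. Every participant must have internet access and a device to be eligible, so a virtual patient can open the form as soon as the call ends. Payment, the number of contacts and the reminder window are the same in both arms. Forms carry identification numbers, not names (section E), and no text says the treating provider sees individual answers. The preference wording covers all questionnaires, including the provider's own, so it may only mean that each respondent chooses the mode for their own form. Offering two modes may also help response.

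All of this stands, and it limits the claim: the arms may differ in mode, place and delay, but the documents do not show that they will, or by how much. It does not remove the point, because no text makes the procedure common and the listed data would not show whether it was.

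Two stronger readings are tempting. A reader might infer that office forms will almost all be captured on site while virtual forms will mostly come in after a reminder. No text supports either. A reader might also infer that selective non-response in the virtual arm would seriously inflate false noninferiority. The shift in a respondents' mean is the fraction lost times the gap between responders and non-responders. At the planned attrition of about 5%, confined to the virtual arm, a shift of 0.5 to 1 point needs a gap of 0.5 / 0.05 = 10 to 1 / 0.05 = 20 points, which is 1 to 2 SD at SD 10. Nothing in the documents suggests a gap that large.

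**Conclusion.** The concern holds as a gap in the measurement procedure for the primary outcome. The plan allows the mode, place and delay of PSQ-18 completion to differ by arm and lists no data that would show whether they did. It does not establish that a bias exists, nor its direction. If answering in the clinic raises office scores, the comparison works against noninferiority; if it lowers them, it favours noninferiority.

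The figures are illustrations that rest on an assumed setting effect, 50 evaluable patients per arm, SD 10 and the two-sided 95% confidence interval rule. They show only that 1 or 2 points would matter: about 70% falling to about 51% or 32% at no true difference, or 2.5% rising to about 7% at a true difference of -5 with 1 point in the virtual arm's favour. The change is worth making because it is cheap and uses what the trial already requires. The sample size is unaffected.

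**What to change.** In the Study instruments and Postoperative Visit (6 weeks) texts, replace the preference rule for the PSQ-18 with one procedure. Send every participant in both arms the same REDCap link at the same time after the visit, for completion away from the clinic. Allow paper only as a take-home or mailed form, on the same terms in both arms. Align the statement that instruments are administered at the visit with this.

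Add date, mode and place of PSQ-18 completion to the six-week data list. In Statistical Analysis, add a sensitivity analysis of the primary difference by mode and timing of completion. Both are set after randomisation, so this analysis is a check on robustness, not a correction.

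Cost: protocol wording, three data fields and one extra analysis. REDCap, the reminders and the internet requirement are already in the plan. Some office forms that would have been collected on site will need a reminder, so office-arm response may be slower or slightly lower.
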